Design	
The study is designed as an open-label, single arm cohort study, to evaluate the Acceptability, safety and Use of daily oral PrEP (FTC/TDF) in 150 adolescents (approximately 75 participants at each site), ages 15-19 years, their adherence to study product, and any changes in their sexual and health behaviors over a 12-month (52 week) period. All participants will complete an initial (12 week) 3- month period, during which they will receive PrEP as part of a combination prevention package. At all subsequent visits, participants will be offered the opportunity to hear real-time feedback of drug level data as part of their adherence counseling or they may choose to have adherence counseling without the feedback of drug level data. The decision about feedback as well as self reported adherence will be captured via interviewer administered questionnaires at each follow up visit. At the first 3 month (week 12) visit and 3 monthly (weeks 24, 36, 48) intervals thereafter participants will be offered the following options: full package + PrEP, stop PrEP and continue with rest of package or alternatively re-start PrEP if previously stopped. This will occur during protocol-specified study visits.
 
Participants will be followed regardless of PrEP usage for a total of 12 months (52 weeks). PrEP may be stopped at any other clinic visit but recommencement can only occur at a scheduled visit when all medical criteria are met including a negative HIV test. Adherence counselling will be offered at every visit with options to have drug level feedback or not as part of this counselling.

Study site	The study will be conducted at The Desmond Tutu HIV Foundation research site in Masiphumelele, Cape Town and the Perinatal HIV Research Unit (PHRU) site in Soweto, near Johannesburg.
Study drugs	FTC/TDF or Truvada® is a 200mg/300mg fixed dose combination tablet containing emtricitabine (FTC) and tenofovir disoproxil fumarate (TDF).
Study population	Healthy, HIV-uninfected adolescents, 15 and 19 years of age
Number of participants	150 enrolled participants (approximately 75 participants at each site)

Treatment Regimen	Participants will be provided with a supply of FTC/TDF tablets, taken orally, once daily for first 3 months. Thereafter, these tablets will only be supplied to those who indicate willingness to take PrEP and who do not have a clinical contraindication to do so.

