The rationale for this study design is based on some of the feedback received from the VOICE and FEMPREP studies. Women in these studies reported high PrEP usage, remained in study and yet drug levels indicated very poor PrEP usage (Marazzo et al CROI 2013). Some rationale for this has been that PrEP acceptability was low, but with a keen perception among participants that study participation hinged on pill adherence. Thus, despite information that drug levels would be assessed, participants chose to report pill usage falsely. By making it very clear that trial participation does NOT hinge on PrEP usage (other than the first 3 months) we hope that we will get a more accurate assessment of real PrEP usage. We also hope that if participants really want to be taking PrEP, that adherence to product will persist. Other open label studies such as iPrEx OLE suggest this may be the case. By designing the study with an “opt out” arm we hope that we will create an authentic comparator group for participants taking oral PrEP (FTC/TDF) persistently and adherently, in order to assess any significant differences in adolescents taking oral PrEP (FTC/TDF) versus those who choose NOT to do so. We recognize that these may include demographic differences but may also include perceptions of risk, sexual activity, etc. In addition, we hope that this will give us a true sense of pill usage among this population- data that is currently unknown and required in order to more accurately model the impact of this intervention in this age group.

Both groups will be treated equally, except for administration of TDF/FTC therapy to those who select to include PrEP in their prevention package.

It was felt by the protocol team that the question of use and acceptability would best be answered by employing an open label design. The three month initial phase will mean that everyone will at least be exposed to 3 months of PrEP usage.

Adherence to medication can be measured in different ways depending on the condition and the

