3.2 SECONDARY OBJECTIVES

- To evaluate adherence to a daily regimen of oral PrEP (FTC/TDF), as a component of a comprehensive HIV prevention package for adolescents between 15 and 19 years of age.
- To evaluate change in sexual activity, perceptions of sexual risk, risk compensation, and health behaviours, including condom use, in adolescents, between 15 and 19 years of age, who take a daily regimen of oral PrEP (FTC/TDF) over a 12 month period.
- To assess study participants' and their partners' perceptions on key issues associated with oral PrEP (FTC/TDF), including adherence barriers, adherence facilitators, and general product knoweldge, as part of a comprehensive HIV prevention package [with HIV testing, STI management, risk reduction counseling, access to condoms, PEP, counseling and referral for male circumcision(for boys)].
- Incidence of HIV infection, as measured by seroconversion of study participants during the approximate 12 months (52 weeks) of follow-up.

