binary and continuous constructs will be analysed at each study visit (repeated measures) and in the overall study period (through aggregation of measures from each study visit). The analysis for this primary endpoint is largely descriptive, with the estimates of adherence and their 95% confidence intervals reported for different adherence measures for the cohort overall as well as a priori subgroupings by age, gender and sexual activity during the study. Subsidiary analyses will develop models to examine the predictors of adherence within the cohort; given the sample size, such analyses will have limited statistical power and should be considered exploratory. For repeated measures of adherence from each study visit, we will use a generalized linear modelling approach that includes fixed effects (e.g., participant characteristics) and random effects (e.g., characteristics of study visits). Following the GLLAMM routine in Stata, this will include mixed-effects linear models (for continuous measures of adherence) with maximum-likelihood extensions to binary adherence endpoints. (Skrondal A, Rabe-Hesketh S. Generalized latent variable modeling: multilevel, longitudinal and structural equation models. Boca Raton: Chapman and Hall, 2004.)

This approach converges with that of generalized estimating equations based on the Huber-White sandwich variance estimator.

2a. Secondary: Sexual Activity

Reported number of steady and casual sex partners, condom use (and change after introduction of study product), substance use prior to or during sex, as evidenced by participant responses to interviewer-administered questionnaires

Analysis plan:

The key analysis question for this secondary endpoint is whether different measures of sexual risk change with the availability and/or uptake of PrEP (in the initial 3-month mandatory study follow-up period) compared to periods “off-Prep”. The measures of sexual risk include continuous measures (number of sexual partners) as well as binary measures (casual sex partners yes/no, substance use prior to sex, consistent condom use during sex).

All measures are visit-specific, with a maximum of 12 measures during the study, per

CHAMPS: Choices For Adolescent Prevention Methods for SOUTH AFRICA

Pilot study B: “PlusPills”

A Demonstration Open Label Study to Assess the Acceptability and Use of Truvada Pre-exposure Prophylaxis in Healthy, HIV-Uninfected Adolescents, 15-19 Years of Age.

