participant. In analysis, we will first use graphical approaches to display the proportions of participants reporting binary sexual risk behaviours (or means of continuous measures) at each study visit over the 12-month period. Following this, we will use repeated measures methods (as described above) for both binary and continuous dependent variables, with PrEP access treated as a binary variable distinguishing visits in on vs. off PrEP phases; in the first instance, these models will not include other covariates.

2b. Proportion of scheduled HIV testing appointments that are missed, in relation to individual characteristics (age, sex, number of partners, use of other prevention methods) and the characteristics of the product.

Analysis:

“Missed appointments” will be defined as participants being >7 days late for a visit scheduled on a 28-day cycle. This measure will be analysed as a binary variable following the repeated measures approaches described above.

3. Secondary: HIV Incidence

HIV infection, as measured by seroconversion of study participants during the approximate 12 months of follow-up

Analysis:

The incidence of HIV will be described using person-time (rates per 100 person years of observation) and product-limit (survival proportion) approaches. For both methods, the date of seroconversion will be the midpoint of the interval between the last negative and first positive HIV test. For participants lost to follow-up, the date of censoring will be one day after the last visit attended.

C. Exploratory Endpoints:

1. Exploratory: Dried Blood Spot/plasma biofeedback

Correlation of self reported adherence and presence of drug levels in participants who are tested using plasma drug levels or DBS and received results compared to participants who are tested using plasma/DBS but do not receive biofeedback of results.

CHAMPS: Choices For Adolescent Prevention Methods for SOUTH AFRICA

Pilot study B: “PlusPills”

A Demonstration Open Label Study to Assess the Acceptability and Use of Truvada Pre-exposure Prophylaxis in Healthy, HIV-Uninfected Adolescents, 15-19 Years of Age.

Analysis:

These data will be described as proportions at each study visit; while we will calculate differences in proportions attending between participant who do and do not receive biofeedback results, no formal statistical tests will be used for this exploratory endpoint.

2.Exploratory: Sexual behaviour by coital diaries

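### The planned on/off-PrEP model for sexual risk mixes who chooses PrEP with change within a participant, and ties both to study time

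*SAP*

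**What the plan says.** The objective in Protocol 3.2 is "To evaluate change in sexual activity, perceptions of sexual risk, risk compensation, and health behaviours" in adolescents taking PrEP over 12 months. SAP B.2a turns this into the question whether measures of "sexual risk change with the availability and/or uptake of PrEP (in the initial 3-month" mandatory period), compared with periods off PrEP. The exposure is "PrEP access treated as a binary variable distinguishing visits in on vs. off PrEP phases". On adjustment, the SAP adds that "in the first instance, these models will not include other covariates", and names no later adjusted model.

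The repeated-measures method is carried over from the adherence analysis (SAP B.1). There the only illustration of what varies randomly is "random effects (e.g., characteristics of study visits"), and the approach is said to converge with GEE and a sandwich variance. A participant intercept is not mentioned.

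On who is on or off, the Protocol Summary (Design) lets participants from week 12 continue, or "stop PrEP and continue with rest of package or alternatively re-start PrEP if previously stopped". Protocol 2.5 says of the differences between those who take PrEP and those who do not that "these may include demographic differences but may also include perceptions of risk, sexual activity, etc".

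**The concern.** The question is about change, which is a contrast of the same adolescent on and off PrEP. After week 12 the off visits come from those who chose to stop and the on visits from those who chose to stay. If riskier adolescents tend to stay on, a single uncentred on/off term shows higher risk on PrEP even when nobody's behaviour has changed. If less risky adolescents stay on, it shows the reverse. The protocol itself expects such a difference between the two groups, but the model has no term for it.

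There is a second, separate problem. Everyone is off at Day 0 and on at weeks 4 to 12, and off status otherwise gathers late in follow-up. Any general trend in sexual risk, for instance from the risk-reduction counselling given at every visit, therefore also enters the on/off coefficient.

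At stake is the study's reading on risk compensation, which Protocol 2.6.7 says the study was designed to evaluate.

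**Working it through.** **1. The plan's own figures.** The sample size reproduces: 135/(1 − 0.10) = 150. No effect size, power, within-participant correlation or expected opt-out rate is given for sexual risk, so the size of the problem can only be shown under assumptions.

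**2. Where on/off status varies** (questionnaires from Protocol Table 1; product supply from Protocol 7.4):

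| Questionnaire | PrEP status | Differs between participants? |
|---|---|---|
| Day 0 | off | no |
| Weeks 4, 8, 12 | on (mandatory phase) | no |
| Weeks 24, 36, 48 | chosen | yes |
| Week 52 | taken as off: 7.4 offers no product at week 48 | no |

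That is 1 + 3 + 3 + 1 = 8 questionnaires, against the maximum of 12 stated in B.2a. Selection can act at 3 of the 8.

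**3. What the coefficient estimates.** In a linear model with one uncentred indicator,

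b = w × b(within) + (1 − w) × b(between).

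b(within) is the change sought. b(between) compares participants with more and fewer on-PrEP visits, and is zero only if choice is unrelated to underlying risk. Modelling within-participant correlation raises w but does not bring it to 1. A sandwich variance corrects the standard error and leaves the mixture as it is.

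**4. Simulation with no PrEP effect.** Assumed inputs:
- 150 participants on the 8 visits above, with underlying risk u ~ N(0,1).
- Risk behaviour at a visit: probability expit(−0.4 + 1.2u).
- On PrEP at weeks 24, 36 and 48: probability expit(0.2 + s·u), with s = 0.5 or 1.0.
- Linear GEE, sandwich standard errors, two-sided 0.05.

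Ranges span separate runs.

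| Model | Spurious difference, s = 0.5 / 1.0 | False positives, s = 0.5 / 1.0 |
|---|---|---|
| PrEP only, exchangeable | +1.2 to +1.3 / +2.3 points | 7–9% / 14–17% |
| PrEP only, independence | +4.1 points (s = 0.5) | 33% (s = 0.5) |
| PrEP + visit, exchangeable | – | 14% / 36% |
| Participant's proportion on PrEP + visit: within coefficient | – | 4% / 6% |

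With no selection, every model rejected 4–7%. Visit terms alone make matters worse because the contrast then rests on weeks 24 to 48, the self-selected visits.

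**5. Study time.** Add an assumed secular fall in risk of 0.6 to 0.9 log-odds per year, with s = 0.5 and still no PrEP effect. The within-participant coefficient without a visit term is off by +2.4 to +3.6 points and rejects 14–29%. With visit in the model, rejection returns to about 6%. A separate run gave 25.5% without visit and 4.4% with it.

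**6. Second check, continuous outcome.** Assumed: 135 participants, intraclass correlation 0.5, 40% off PrEP at the choice visits, choosers about 0.65 SD higher in underlying risk, 8 visits, true effect zero.
- Pooled, no participant effect: 0.17 SD, 88% false positives.
- Participant random intercept: 0.02 SD, 7%.
- Intercept plus the participant's mean on-PrEP share: 0.00 SD, 5%.
- The last model under an added fall of 0.3 SD per year: 35% without study time, 5% with it.

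**The case against.** **The bias is small on the real schedule.** Five of the eight questionnaires have the same status for everyone. With a participant intercept or exchangeable correlation, the PrEP-only model is off by only 1 to 2 points. This stands, with one reservation: the plan names no participant effect, and without one the error is several times larger.

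**Larger figures can be produced but do not describe the plan.** A simulation that stops at week 48 gives up to 25% false positives, and 45% once visit terms are added. A reader might infer that the planned analysis misleads that often. The documents do not support this: the questionnaire is scheduled at week 52, and B.2a plans no visit terms.

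**The plan makes no causal claim.** A reader might infer that self-selection will be reported as behaviour change caused by PrEP. The SAP asks only whether risk changes with availability or uptake, its wording marks the model as a starting point after graphical display, and Protocol 2.5 admits the groups may differ. This stands. What does not follow is that a later model will deal with it, since none is specified.

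**The exposure is not settled.** The parenthesis in B.2a can be read as limiting on to the mandatory 12 weeks, where nobody selects. If every later visit then counted as off, selection would drop out, but the indicator would be a function of study time alone. If only genuinely off visits formed the comparison, selection would return through who supplies them. Week 52 is also open: the Protocol Summary lists week 48 among the decision visits, while 7.4 offers no product then. The ambiguity is a reason to define the term and does not answer the point.

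**Conclusion.** The point holds as a gap in specification with a modest effect on a secondary endpoint. As written, one coefficient carries three things: self-selection into PrEP, change within a participant, and study time. Only the second answers the objective.

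Under no PrEP effect, on all 8 questionnaires and with exchangeable correlation, the spurious difference is about 1 to 2 percentage points with 7–17% false positives against a nominal 5%. If no within-participant correlation is modelled, it is about 4 points and 33% at the weaker selection. It also grows if visit terms are added without separating within from between. These sizes rest on assumed selection strength, opt-out rate and outcome variation, none of which is in the documents.

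The direction is unknown. Only selection of riskier adolescents into PrEP was simulated, and the opposite selection would reverse the sign. The documents therefore do not support predicting a false finding of risk compensation rather than a false reassurance.

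**What to change.** Amend SAP B.2a, and Protocol 10.6 to match, as follows.

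- Name a participant random intercept. Add each participant's own proportion of visits on PrEP as a covariate, **and** visit (or study time) as a fixed factor. Participant fixed-effect models (conditional logistic or Poisson) with visit terms are an alternative; the proportion then drops out. The visit term is needed in either case: without it the within-participant estimate still picks up any trend in risk (working, step 5).
- Define which visits count as on PrEP, including chosen visits after week 12 and the week 52 visit, and reconcile the stated 12 measures with the 8 scheduled.
- Report the within-participant coefficient as the estimate of change. Call it an association, because an adolescent may stop PrEP after a change in her or his own risk, and no term above removes that.
- Report the between-participant coefficient separately, as a description of who chooses PrEP.

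The change needs no new data. It costs SAP wording and a wider confidence interval, because the estimate then leans on participants whose PrEP status changes.

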7.2 ENROLLMENT VISIT

Day 0 for the participant will be the day of the Enrollment Visit:

- Administrative/Behavioural Procedures

- Locator information (update)
- Review of study procedures (ongoing consent)
- HIV pre-and post-test counseling, including risk reduction counselling
- Provision of condoms
- Eligibility assessment (including review of all screening documentation)
- Baseline sexual risk behavior questionnaire (for all enrolled participants)
- Reimbursement
- Schedule next visit (if applicable)

- Clinical Procedures
 - Review of all prior screening documentation
 - Update medical history and/or current medications, if applicable
 - Re-confirmation (by participant self-report) of medical eligibility information
 - Syndromic treatment for STI, if clinically indicated
 - Offer of STI testing and treatment for participant and partner(s) if indicated
 - Confirmation of current contraceptive method and contraceptive counseling
 - Contraceptive counselling and provision of contraception as appropriate
 - Disclosure of available test results, which must be made available to participant prior to administration of study product
 - Hepatitis B vaccination, if indicated
 - Update Medical History
 - Provision of study drug and instructions

- Laboratory Procedures
 - Urine pregnancy testing (for females)
 - HIV rapid testing
 - At all visits
 - As clinically indicated

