7.12 BIOHAZARDOUS WASTE

The Principal Investigator will ensure that biohazardous waste will be contained according to institutional, transportation/carrier, and all applicable regulations.

Table1: Schedule of Study Visits and Procedures**Nb. Screening visit (up to -4 weeks); Enrollment (0 weeks); Final visit (52 weeks).**

Visit week	Prior	Screening	Enrolment	4	8	12	24	36	48	Final 52
Obtain written informed consent for screening and enrolment, from participant and his/her guardian		X								
Assessment of understanding for ICF		X								
Identification number assignment		X								
Locator information		X	X	X	X	X	X	X	X	X
HIV pre-and post-test counselling		X	X	X	X	X	X	X	X	X
Eligibility assessment (including review of all screening documentation)			X							
Sexual risk behavior questionnaire			X	X	X	X	X	X	X	X
Acceptability questionnaire				X	X	X	X	X	X	X
Adherence assessment and counselling				X	X	X	X	X	X	
Feedback of DBS or plasma results to those who agree to this.				X	X	X	X*	X*	X*	
Provision of condoms, condom counselling and rest of prevention package (bar PrEP)		X	X	X	X	X	X	X	X	X
Study product supplies and instructions *Only to those who indicate willingness to use.			X	X	X	X*	X*	X*		

Visit week	Prior	Screening	Enrolment	4	8	12	24	36	48	Final 52
Reimbursement	X	X	X	X	X	X	X	X	X	X
Schedule next visit (if applicable)		X	X	X	X	X	X	X	X	*
Focus group (including assent/consent)	X									X
Obtain/update medical history		X	X	X	X	X	X	X	X	X
Conduct physical exam		X	*	*	*	*	*	*	X	*
Incl TS at enrollment and week 48										
Disclose available test results		X	X	X	X	X	X	X	X	X
Provide or refer for contraception		X	X	X	X	X	X	X	X	*
Contraceptive counseling		X	X	X	X	X	X	X	X	X
Record/update AEs including social harms/benefits			X	X	X	X	X	X	X	X
Treat or prescribe treatment		*	*	*	*	*	*	*	*	*
Syndromic treatment for STIs										
Hepatitis B sAb/sAg testing		X								
Hepatitis B vaccination		*	*				*			
HIV serology		X	X	X	X	X	X	X	X	X
Herpes (HSV-2)		X				X			X	
Chlamydia, and Gonorrhea testing.										
Females low vaginal self-swab		X				X			X	
Males Urine										
Serum chemistries		X				X	X	X	X	
Creatinine Clearance										X
ALT/AST serology		X				X	X	X	X	X
Haematocrit				X	X					X
Full Blood count		X				X	X	X	X	
Measurement of study drug levels (DBS and plasma for drug levels)				X	X	X	X #	X #	X #	X #
Measurement of study drug levels by DBS only										X #

Visit week	Prior	Screening	Enrolment	4	8	12	24	36	48	Final 52

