participants. Should the SMC or the PSRT detect evidence of harm such that the recommendation for halting or modifying the study is made, then this will be communicated to the PI, The protocol team and the DAIDS prevention division. The IRB and MCC will also be informed of the discontinuation of the study and/or the modification and reasons for modification of the study. All further enrollment, and study activities other than safety follow up will be put on hold. Participants, guardians and CABS will be notified as soon as possible after next steps are identified.

DATA ANALYSIS PLAN

A customized data entry and management system will be implemented for the project in Microsoft Access. Data will be analysed using the statistical programme STATA (Stata Corporation, College Station, Texas, USA). Simple descriptive statistics including frequency distributions will be used to assist in data cleaning and summarization.

The analysis plan for each of the study objectives (per 10.2 above) is detailed below. (Note that throughout the analysis, all statistical tests will be 2-sided using an alpha of 0.05.)

Endpoints:

A. PRIMARY

1. Primary: Use

Number of adolescents who continue to use PrEP after the initial 3 month period and the total time on PrEP for each adolescent and for the cohort as a whole.

Analysis:

Proportions of participants (a) willing to use and (b) taking up PrEP will be described with point estimates and exact 95% confidence intervals. “Remaining on PrEP” will be defined as any self-reported use of PrEP at each study interval (regardless of adherence) over the 9-month follow-up period, as a binary outcome. The first 3-month “use” will be 100% for all 150 participants. We will use product-limit methods to examine ‘survival’ proportions for

CHAMPS: Choices For Adolescent Prevention Methods for SOUTH AFRICA

Pilot study B: “PlusPills”

A Demonstration Open Label Study to Assess the Acceptability and Use of Truvada Pre-exposure Prophylaxis in Healthy, HIV-Uninfected Adolescents, 15-19 Years of Age.

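### The only on/off-PrEP model that the SAP commits to for sexual risk has no time term, and the coding of Day 0 and week 52 is not stated

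*SAP*

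**What the plan says.** SAP B.2a (Sexual Activity), repeated in Protocol 10.6, sets as its key question "whether different measures of sexual risk change with the availability and/or uptake of PrEP" in the initial 3-month period, compared with periods off PrEP. Measures are first plotted by visit. Repeated-measures models follow, with PrEP access as a binary variable "distinguishing visits in on vs. off PrEP phases; in the first instance, these models will not include other covariates". The method is carried over from SAP B.1, which describes mixed models with "random effects (e.g., characteristics of study visits") given as an example. SAP A.1 states that use in the first 3 months "will be 100% for all 150 participants".

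On Day 0, Protocol 7.2 schedules a "Baseline sexual risk behavior questionnaire (for all enrolled participants"), and the endpoint wording includes "condom use (and change after introduction of study product"). The model text does not say whether the Day 0 record is an off-PrEP observation.

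On week 52, the protocol is not consistent. Section 7 ends the optional product period at week 48, and 7.4 lists supply at weeks 12, 24 and 36 and says none is offered at week 48. The Protocol Summary lists week 48 among the visits where the PrEP choice is offered and schedules product for 52 weeks. Section 7.6 places routine withdrawal at week 52, and 7.8 takes a week 52 level from those still on product.

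B.2a gives a maximum of 12 measures per participant. B.2b defines a missed HIV test by reference to visits on a 28-day cycle.

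**The concern.** If everyone is on PrEP at weeks 4, 8 and 12 and can be off only later, an on/off contrast without a time term is partly a contrast of early with late visits. Any drift in reported risk then enters the PrEP coefficient. Drift is plausible: counselling and condoms are given at every visit, and Protocol 2.6.7 cites an earlier PrEP study in which condom use rose from 52% at screening to 92% at months 3, 6 and 9 and 95% at month 12.

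Day 0 and week 52 lie at the two ends of the time axis, so where they are placed matters. Two analysts could follow the same SAP text and report different answers on risk compensation from the same data.

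**Working it through.** **The SAP's own figure first.** Twelve measures would fit 28-day visits from week 4 to week 48 (48/4 = 12). In Protocol Table 1 the "Sexual risk behavior questionnaire" row is marked at enrolment and weeks 4, 8, 12, 24, 36, 48 and 52, which is 8. For 150 participants that is at most 150 × 8 = 1,200 records, not 150 × 12 = 1,800. The gaps are 28, 28, 28, 84, 84, 84 and 28 days, so a 28-day cycle does not describe weeks 24, 36 and 48. Protocol 7.3 and 7.4 apply a window of 7 days either side of target to the 12-weekly visits too.

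**Inputs for the crude odds ratio.** From the documents: 150 participants, the visit weeks, and all on PrEP at weeks 4 to 12. Assumed: 20% of current users stop at each of weeks 12, 24 and 36 with no restart, giving on-PrEP shares s = 1, 1, 1, 0.8, 0.64, 0.512 at weeks 4 to 48; no PrEP effect; the risk trends below. Off-PrEP visits at weeks 4 to 48 are 150 × (0.2 + 0.36 + 0.488) = 157 of 900, none before week 24.

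**Formula.** Mean on-PrEP risk = Σ s·r / Σ s. Mean off-PrEP risk = Σ (1 − s)·r / Σ (1 − s), with Day 0 and week 52 added to the off group, each with weight 1, where coded off. The odds ratio is odds(on)/odds(off).

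**Linear fall, 40% at Day 0 to 25% at week 52.** Risks at weeks 4 to 48 are 0.3885, 0.3769, 0.3654, 0.3308, 0.2962 and 0.2615.
- On: 1.719/4.952 = 0.347.
- Off, Day 0 excluded and week 52 off: (0.3004 + 0.25)/2.048 = 0.269; OR 1.45.
- Off, both excluded: 0.3004/1.048 = 0.287; OR 1.32.
- Off, both coded off: (0.3004 + 0.40 + 0.25)/3.048 = 0.312; OR 1.17.
- Off, Day 0 off and week 52 excluded: (0.3004 + 0.40)/2.048 = 0.342; OR 1.02.

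**Drop to 25% by week 4, then flat.** On-PrEP risk is 0.25. Off-PrEP risk is 0.25 when Day 0 is excluded, (0.262 + 0.40 + 0.25)/3.048 = 0.299 with both off, and (0.262 + 0.40)/2.048 = 0.323 with Day 0 off and week 52 excluded.

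| Trend in risk | Day 0 excl., wk 52 off | Both excl. | Both off | Day 0 off, wk 52 excl. |
|---|---|---|---|---|
| Linear 40% to 25% | 1.45 | 1.32 | 1.17 | 1.02 |
| Linear 40% to 35% | 1.12 | 1.09 | 1.05 | 1.01 |
| Drop to 25% by week 4, flat | 1.00 | 1.00 | 0.78 | 0.70 |
| No trend | 1.00 | 1.00 | 1.00 | 1.00 |

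Coding week 52 by the participant's last choice (51% on) under the steep linear trend gives 1.35 with Day 0 excluded and 1.06 with Day 0 off.

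**Varying the opt-out share.** A separate simulation under the null used off-PrEP shares at weeks 24/36/48 of 10/15/20% or 30/45/60%, also with the last-choice coding. The odds ratio ranged over 0.99–1.02 with no drift, 0.94–1.21 with a log-odds drift of −0.4 over 52 weeks, and 0.90–1.46 with −0.8. At 10/15/20% off and drift −0.8, it was 0.90 or 1.44 depending only on coding.

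**Rejection rates at 5% under the null** (logistic GEE, 150 participants, stopping unrelated to risk, codings in table order). Unadjusted: 89, 48, 34 and 5% for the steep linear fall; about 3, 7, 64 and 80% for the early drop; about 6–20% for 40% to 35%. Adjusted for categorical visit: about 3–6%.

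**The case against.** The SAP does not stop at this model. Plots by visit come first and would show a trend, the wording of the covariate sentence leaves room for later models, and a visit-level random effect is mentioned. In a simulated mixed model for a continuous outcome (assumed drift 0.45 residual SD), such an effect cut false rejections from 95/65/45/7% to 43/17/5/3%. That help is material but partial, and the SAP offers the effect only as an example. A plot does not settle the coding. The protocol also lets participants stop at any time, so real use in weeks 4 to 12 may be below 100%. That weakens the confounding without removing it.

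The endpoint is secondary and self-reported in a single-arm study, and the trend is assumed. This stands and limits the weight of the point.

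Adjustment does not cure self-selection. Of differences between those who take PrEP and those who choose not to, Protocol 2.5 says: "We recognize that these may include demographic differences but may also include perceptions of risk, sexual activity, etc". When stopping depends on underlying risk, simulated rejection under the adjusted model is 14–16% (shift of 0.5 in log-odds per SD) or 32–42% (shift of 1.0). A within-participant model holds 4–6% there, but about 16% if stopping follows the behaviour reported at the decision visit.

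A reader might infer that coding Day 0 as off and excluding week 52 makes the bias negligible. That holds for a linear trend only; under the early drop, the shape of the condom data in Protocol 2.6.7, it is the worst of the four. Nor does the 89% figure describe this trial: it belongs to one coding with the steepest trend tried.

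**Conclusion.** The concern holds as a gap in specification. The one committed model confounds PrEP status with time, and two undefined codings can move the crude odds ratio from 1.45 to 1.02 under one assumed trend and from 1.00 to 0.70 under another, with no PrEP effect in either. No coding is safe for every trend shape. The size rests on the assumed trend and opt-out share, neither of which the documents give; with no trend there is no bias from this source.

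The documents do not support saying that the planned analysis is invalid, that adjusted models are ruled out, or that a time term alone would give a causal answer. The figure of 12 measures and the 28-day cycle are wording errors: the 7-day limit for a missed test agrees with the protocol's visit window. Overall this is a minor, cheap improvement to a secondary analysis. The sample size is unaffected.

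**What to change.** 1. State in B.2a whether Day 0 is an off-PrEP observation, a separate baseline or excluded. Reconcile the Protocol Summary and sections 7.6 and 7.8 with the section 7 visit list and 7.4 on product between weeks 48 and 52, then state how week 52 is coded (last choice, off or excluded).
2. Keep the unadjusted model, which is closest to the SAP's question about the initial 3 months. Beside it report, as a sensitivity analysis, a model of post-baseline visits only, with scheduled visit as a categorical term and Day 0 risk as a covariate, not an outcome row. Linear weeks are not a substitute: with Day 0 kept as an off-PrEP row, a linear week term gave about 90% false rejections under the early drop.
3. State that the adjusted contrast compares self-selected stoppers with continuers after week 12, is less precise, and stays biased if stopping depends on risk. A within-participant model with the same visit terms is optional. No single model should carry the conclusion.
4. Wording only: replace 12 measures with 8, and define a missed test as more than 7 days after each scheduled target date.

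Cost: SAP text and one extra model, or two with the optional check; no new data. The simulated standard error of the log odds ratio is 0.11–0.19 unadjusted, about 0.24 visit-adjusted and 0.32–0.34 within-participant, with stopping unrelated to risk.
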